1.8 Justification of Pooling Across Devices

Pooling data from subjects with different internal devices (CI24RE, CI512, and CI532) will be done based on the following: all devices included in this study use a perimodiolar electrode and are similar in function, and the co-primary efficacy endpoints are based on within-subject comparisons for which the device remains constant.

Consistency of the primary efficacy endpoints will be assessed by testing for a difference across devices in the difference between FAST and ACE for CNC word recognition and BKB sentence reception in noise. Testing will be conducted via an analysis of variance model, with difference between FAST and ACE as the outcome and device as the factor. A p-value for the device factor of less than 0.15 will be considered evidence of differences across devices for one of the primary efficacy endpoints. If there is evidence of a difference, additional analyses will be performed to explore the possible role of baseline characteristics to explain the results. Results for the primary efficacy endpoints will also be presented separately by device, irrespective of the test of differences across devices, to help understand both qualitative and non-significant differences across devices.

1.9 Missing Data

All efforts will be put forth to ensure near complete follow-up, with particular focus on the assessment of the primary outcomes and occurrence of adverse events. A reminder of subject follow-up due dates will be provided to participating centers to facilitate scheduling of the follow-up visits.

Sensitivity analysis will be conducted to address the potential impact of missing endpoint data using a multiple imputation analysis with 10 imputed datasets. A separate imputation model will be performed for each primary outcome variable (CNC score and average SRT). The predictor variables in the model will include, but are not limited to, the three target variables in the primary endpoint analysis (treatment, period, and sequence), and five auxiliary variables to improve the estimation of missing datapoints (Reading Span score, age, duration of hearing loss, pre-operative sentence score, and duration of hearing aid use). The imputed datasets will then be combined for inference using standard methods such as those available in SAS PROC MIANALYZE or other valid statistical software.

Design Overview	The design is a within-subject, repeated-measures take-home study. Adult cochlear-implant recipients will be given two different sound coding strategies, FAST and ACE, for take-home use in a crossover design. The period of time with each strategy will be 3 months, for a total of 6 months of participation post initial activation. Study procedures will include mapping, speech perception, sound quality judgments, a questionnaire, cognitive testing, and battery logs.
Primary Objective	
 1. To determine if FAST is non-inferior to ACE for word recognition in quiet in newly-implanted cochlear-implant recipients. 2. To determine if FAST is non-inferior to ACE for sentence perception in noise in newly-implanted cochlear-implant recipients.
Primary Endpoint	
 1. Word recognition in quiet will be non-inferior for FAST compared to ACE. 2. Sentence perception in noise will be non-inferior for FAST compared to ACE.
Secondary Objectives	
 1. To quantify the battery life benefit for FAST compared to ACE. 2. To obtain insight into sound quality differences between the strategies and the relative difficulty of conversion for the cochlear-implant recipient from ACE to FAST versus FAST to ACE.
Secondary Endpoints	
 1. Duration of battery life will be superior for FAST compared to ACE. 2. Comparative ratings on a hearing questionnaire will not be significantly different between the two experimental groups.
Study Intervals	Primary data points are at 3 months and 6 months post-activation.

CONFIDENTIAL

IDE #G150140 V2.4 September 28, 2017

Page 6 of 24

CAM-CL-111_F

Rev. 1

Abbreviations

Term	Definition
ACE	Advanced Combination Encoder strategy
ADRO	Adaptive Dynamic Range Optimization
AE	Adverse Event
ASC	Automatic Sensitivity Control
BTE	Behind-the-ear
CP810	Behind-the Ear Cochlear Processor 800 series
CP900	Behind-the Ear Cochlear Processor 900 series
CP1000	Behind-the Ear Cochlear Processor 1000 series
CRF	Case Report Form
FAST	Fundamental Asynchronous Stimulus Timing strategy
IA	Initial Activation
IRB	Institutional Review Board
ITD	Interaural timing difference
SAE	Serious Adverse Event
SNR	Signal to noise ratio
SONO	Speech and background noise presented at 0 degrees azimuth
SRT	Speech Reception Threshold

CONFIDENTIAL

IDE #G150140 V2.4 September 28, 2017

Page 7 of 24

CAM-CL-111_F

Rev. 1

1.0 Introduction

The Fundamental Asynchronous Stimulus Timing (FAST) strategy offers excellent potential as a low power alternative coding strategy to the current default strategy in Nucleus® cochlear implants, Advanced Combination Encoder (ACE). Additionally, FAST offers potential bilateral benefits – localization and listening in spatially separated noise – because it has been shown in acute, controlled studies to provide more access to interaural timing difference (ITD) cues (Smith, 2010). FAST outputs a pulse at a time and level that corresponds with the exact time and amplitude of the peak of each envelope cycle. In contrast, ACE uses a fixed pulse rate (default of 900 pulses per second per channel) that bears no relationship to the coded acoustic stimulus.

Previous research with experienced cochlear-implant recipients has shown issues with conversion from ACE to FAST. The FAST strategy typically sounds very different in quality, and acclimatization can be lengthy. This extended adaptation time makes it difficult to show conclusively that FAST is non-inferior to ACE for speech understanding. A potential barrier to evaluating performance with FAST in current cochlear-implant recipients is the extensive amount of prior experience that many recipients have using ACE. Hence, there is a distinct need to evaluate FAST in newly implanted recipients.

The present study will compare speech intelligibility and sound quality with FAST and ACE in a group of 20 newly implanted subjects. There will be a 3-month period of take-home experience with each strategy in a crossover design. The battery life benefit of FAST compared to ACE will also be quantified.

2.0 Study Objectives

Primary Objectives:

1. To determine if FAST is non-inferior to ACE for word recognition in quiet in newly-implanted cochlear-implant recipients.
2. To determine if FAST is non-inferior to ACE for sentence perception in noise in newly-implanted cochlear-implant recipients.

Primary Endpoints:

1. Word recognition in quiet will be non-inferior for FAST compared to ACE.
2. Sentence perception in noise will be non-inferior for FAST compared to ACE.

Secondary Objectives:

1. To quantify the battery life benefit for FAST compared to ACE.

CONFIDENTIAL

2. To obtain insight into sound quality differences between the strategies and the relative difficulty of conversion for the cochlear-implant recipient from ACE to FAST versus FAST to ACE.

Secondary Endpoints:

1. Duration of battery life will be superior for FAST compared to ACE.
2. Comparative ratings on a hearing questionnaire will not be significantly different between the two experimental groups.

2.1 Study Design

The design is a within-subject, repeated-measures clinical investigation.

2.2 Study Procedures

Adult cochlear-implant subjects will be given two different sound coding strategies, FAST and ACE, for take-home use in a crossover design. The period of time with each strategy will be 3 months, for a total of 6 months of participation post initial activation. Study procedures will include mapping, speech perception, sound quality judgments, a questionnaire, and battery logs for both strategies as well as a brief cognitive test. Procedures are described in detail in section 5.0 of this protocol.

2.3 Study Length

The anticipated recruitment time is 6 months. The duration of the study for each subject is 6 months post-activation. The total study duration is expected to be 12 months.

3.0 Device Description

The cochlear implant system that will be used in this IDE study comprises:

- Nucleus® Cochlear Implant
- Nucleus 5 (CP810) Sound Processor, and
- Nucleus Custom Sound™ programming software.

3.1 Implant Description

FDA-approved Cochlear Nucleus CI24RE, CI512, or CI532 cochlear implants will be used in this IDE. There have been no changes to this internal system component.

CONFIDENTIAL

IDE #G150140 V2.4 September 28, 2017

Page 9 of 24

CAM-CL-111_F

Rev. 1

3.2 Sound Processor Description

Commercially available Nucleus 5 (CP810) sound processors will be used in this IDE. There have been no changes to the hardware of the CP810 processor. The CP810 is a behind-the-ear (BTE) sound processor. It is functionally similar to the newer generation Nucleus 6 (CP900 series) and Nucleus 7 (CP1000) processors, but without some of the advanced features (i.e. SmartSound iQ, Wireless Accessories, Data Logging, and iPhone compatibility). The CP810 processor will be loaded with different firmware for the ACE and FAST portions of the crossover study.

3.3 Programming Software Description

The default coding strategy (ACE) and the experimental coding strategy (FAST) will be programmed in the CP810 processor for take-home use with Custom Sound software.

4.0 Subject Population

Adult cochlear-implant candidates capable of completing the study evaluation will be recruited to participate in the IDE. Vulnerable populations will not be eligible for study participation per 45 CFR part 46, subparts A through D as reported by the Investigator.

4.1 Inclusion Criteria

- Medical and audiological candidate for a unilateral CI24RE, CI512, or CI532 series implant
- Post-linguistically deafened
- Native speaker of American English
- Eighteen years of age or older

4.2 Exclusion Criteria

- Previous or existing cochlear-implant recipient
- Pre-linguistically deafened (onset of severe-to-profound hearing loss at less than two years of age)
- Ossification or any other cochlear anomaly that might prevent complete insertion of the electrode array
- Diagnosis of retro-cochlear pathology
- Diagnosis of auditory neuropathy

CONFIDENTIAL

- Unrealistic expectations on the part of the subject regarding the possible benefits, risks, and limitations that are inherent to the surgical procedure and use of the prosthetic device
- Unwillingness or inability to comply with all investigational requirements
- Additional cognitive handicaps that would delay rate of improvement with the cochlear implant

4.3 Release of Medical Information

Subjects will be required to release the exchange of medical information between the Investigator(s) and the Sponsor. This requirement will be clearly identified in the Informed Consent form.

5.0 Investigational Procedures

5.1 Design Overview

This study will implement a within-subject crossover design with 20 subjects. All subjects will receive each of the treatments – the ACE and FAST strategies. In this repeated measures design, half of the subjects, Group 1, will be mapped with FAST first and the other subjects, Group 2, with ACE first, using formalized mapping procedures. Endpoint speech perception testing, additional to standard clinical testing, will be conducted after 3 months of use with the initial strategy. At the 3-month post initial activation (IA) session, each recipient will be programmed with the crossover strategy. The crossover strategy will then be assessed after 3 months of take-home use at 6 months post IA (refer to Table 1). As indicated in Table 1, fine-tuning of the cochlear implant stimulation levels (i.e. MAP) will occur at 1 week and 1 month after receiving each strategy. Standard clinical testing will also occur at 3 months and 6 months post activation.

The order in which the subjects are programmed with the ACE and FAST strategies will be counterbalanced according to group; Group 1 will start with FAST and Group 2 with ACE. Subjects will be randomly assigned to either Group 1 or 2. Standardized programming procedures will be used to program the FAST and ACE strategies. Subjects will be blinded as to the identity of the strategies.

The study design strikes a balance between providing a reasonable amount of take-home experience with each of the strategies and obtaining outcome comparison data for the strategies within the required timeframe. It is acknowledged that maturational effects are not eliminated with crossover to the alternative strategy at 3 months post IA. The exclusion criteria for enrollment will provide control over some of these variables. To further address maturational effects, subjects' scores from the Reading Span Test (a cognitive test of working

CONFIDENTIAL

memory) will be included as a statistical covariate to understand differences in adaptation that might be associated with working memory.

Depending on the Clinical Site, endpoint speech perception evaluations will be conducted either at the Clinical Site or at the Denver Research & Technology Labs (Cochlear Americas). These evaluations will include sentence in noise testing in dynamic four-talker babble and speech-shaped noise. The test setup will be with the target speech and competing noise both presented from a speaker in front of the recipient (S0N0). A speech reception threshold (SRT) will be obtained, which represents the signal-to-noise ratio (SNR) at which the recipient scores 50% intelligibility. Word recognition in quiet will also be conducted.

All subjects will be implanted with a CI24RE, CI512, or CI532 implant and will be given the latest commercially available sound processor. However, recipients will be fit with a CP810 sound processor with no advanced features for the duration of the study (adaptive directionality, wireless accessories, and SmartSound iQ will not be used during study participation).

At the crossover appointment (3 months post IA), endpoint speech perception testing will be conducted with the first strategy. The second strategy will then be programmed for take-home use. Subjects will be asked to acutely rate sound quality with this second strategy in direct comparison to the first strategy. One month after take-home use with the second strategy, subjects will be asked to complete a questionnaire again rating sound quality and speech understanding with the second strategy compared to the first strategy. Comparing the quality of strategy 2 to strategy 1 after a longer period of take-home use with strategy 2 is likely to be less reliable, given reliance on the memory of strategy 1.

Evaluating the sound quality of FAST versus ACE is complex. To minimize memory effects and increase statistical power, a direct comparison of strategies would be ideal. The comparative quality ratings of ACE and FAST at the crossover appointment will provide some insight into sound quality with the two strategies. If the conversion from the initial strategy to the crossover strategy shows larger quality differences for one of the two groups, this may indicate underlying disparities between the two strategies. However, based on previous research with existing recipients, it is known that the sound quality of FAST differs from ACE. The quality and speech understanding questionnaire conducted one month after the crossover appointment will provide further understanding of quality differences after some degree of acclimatization.

Subjects in Group 2 who are initially programmed with ACE and then reprogrammed with FAST at the crossover 3 months post IA will need to be re-programmed with the default ACE program at the final visit 6 months post IA. The ACE map will be fine-tuned at this final visit and will be loaded onto the patient's

CONFIDENTIAL

IDE #G150140 V2.4 September 28, 2017

Page 12 of 24

CAM-CL-111_F

Rev. 1

personal sound processor for take-home use. Instruction will be provided on the use of the processor controls.

The FAST strategy is not currently approved by the FDA as a commercial speech processing strategy that recipients may choose as their clinical strategy for ongoing use. Subjects will be informed prior to enrolling that they will not have the option of continuing to use FAST after the completion of this study. However, this study may provide data for a future submission to seek FDA approval for FAST. In the event that the FAST strategy becomes clinically approved in the future, the current subjects will have access to FAST through their clinical audiologists. At the conclusion of the study, subjects will be provided with the option to upgrade to a compatible sound processor. This option must be redeemed within 5 years from completion of the study.

5.2 Description of Test Measures

5.2.1 Clinical Audiological Testing

Subjects will undergo a standard battery of audiological tests. The clinical data gathered for this study will include frequency-specific thresholds at standard audiometric frequencies (250 – 8000 Hz) and aided speech recognition with AzBio sentences (Spahr et al., 2012) at 60 dBA in the sound field. Audiological data will be gathered pre-operatively and at 3-months and 6-months post IA. CNC word recognition (Peterson & Lehiste, 1962) will also be conducted at the pre-operative candidacy visit.

5.2.2 Device Fitting

Mapping will be conducted using standard clinical procedures. For the CP810 processor that will be used for the duration of this study, the programming clinician will include an Everyday program with ADRO+ASC using standard microphone directionality. The Everyday program will be used for testing throughout the trial. Clinicians may provide other individualized programs as needed for take-home use (e.g., with fixed directional microphones for noisy situations); however, the adaptive directionality mode will not be available. The same feature settings will be used for FAST and ACE. At the conclusion of the study, the subject's personal sound processor will be loaded for take-home use with the range of features that are available at that time.

5.2.3 Sound Quality Ratings

At the crossover visit, acute sound quality ratings will be conducted to compare perceived quality with FAST and ACE at the time of switchover. Immediately after mapping the second strategy, the clinician will read the "Rainbow Passage" and ask the subject to rate his or her perception of the intelligibility, loudness, naturalness, and overall sound quality of the second strategy in comparison to

CONFIDENTIAL

the first strategy. The rating scale will range from unchanged (0) to much better (+5) or much worse (-5).

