5.2.4 Speech Perception (Endpoint Testing)

All speech perception tests will be conducted with recorded materials in a unilateral, implant-only configuration using the subject's Everyday program. The following endpoint speech perception tests will be performed at Cochlear Americas' Research & Technology Labs or at the Clinical Site. The clinician who conducts endpoint speech testing will not be the same clinician who conducts programming for an individual subject, and the testing clinician will be blinded from the subject's group assignment. Thus, the endpoint speech testing will be double-blinded.

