5.5 Postoperative Procedures

5.5.1 Visit 2

Visit 2 will be conducted at the Clinical Sites. Procedures will include initial activation and mapping of the first strategy (Group 1 will receive FAST, and Group 2 will receive ACE). Subjects will be oriented to use of the CP810 processor.

5.5.2 Visit 3

Visit 3 will be conducted at the Clinical Sites. Procedures will include fine-tuning of the initial strategy.

5.5.3 Visit 4

Visit 4 will be conducted at the Clinical Sites. The first battery life questionnaire will be handed out to the subject, and instructions for completing and returning

CONFIDENTIAL

the questionnaire will be provided. Mapping will be conducted for fine-tuning of the initial strategy.

5.5.4 Visit 5

Visit 5 will include endpoint speech perception tests, the Reading Span Test, clinical audiological testing, and programming of the crossover strategy. Depending on the Clinical Site, endpoint speech testing (CNC words and BKB sentences) and the Reading Span Test will be conducted either at the Clinical Site or at the Denver Research & Technology Labs (Cochlear Americas). All programming will be conducted at the Clinical Sites. Since endpoint speech testing will be administered by a clinician blinded to the current treatment, endpoint speech testing and programming will be performed by different clinicians. The crossover strategy will be programmed (Group 1 will receive ACE, and Group 2 will receive FAST), and the acute sound quality ratings will be conducted.

5.5.5 Visit 6

Visit 6 will be conducted at the Clinical Sites. Procedures will include fine-tuning of the crossover strategy.

5.5.6 Visit 7

Visit 7 will be conducted at the Clinical Sites. The SSQ12-C will be completed, and the second battery life questionnaire will be handed out to the subject. Mapping will be conducted for fine-tuning of the crossover strategy.

5.5.7 Visit 8

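### Acute sound-quality ratings follow a live reading, most likely by the programming clinician, with no set level and no matching presentation under the first strategy: a minor weakness with a cheap fix

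*Combined protocol and SAP*

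**What the plan says.** Protocol 5.2.3 sets the procedure at the crossover visit: "Immediately after mapping the second strategy, the clinician will read the" Rainbow Passage, and the subject then rates the second strategy relative to the first on four attributes, from −5 to +5 with 0 as no change. The section mentions no recording, no presentation level, no listening configuration, and no rule on who collects the answers.

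Protocol 5.1 describes the same step: "Subjects will be asked to acutely rate sound quality with this second strategy in direct comparison to the first strategy". Further on it says: "To minimize memory effects and increase statistical power, a direct comparison of strategies would be ideal". It expects some insight from the crossover ratings, and adds that larger quality differences in one group may point to disparities between the strategies.

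Protocol 5.5.4 (Visit 5) puts the ratings in the programming step: "The crossover strategy will be programmed (Group 1 will receive ACE, and Group 2 will receive FAST), and the acute sound quality ratings will be" carried out. Table 1 lists them only under testing at the Clinical Sites.

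Protocol 5.2.4 treats endpoint testing differently: "All speech perception tests will be conducted with recorded materials", with the implant alone. It also separates the staff: "The clinician who conducts endpoint speech testing will not be the same clinician who conducts programming for an individual subject", and the tester is blinded to group.

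Protocol 2.0 gives the second secondary objective: "To obtain insight into sound quality differences between the strategies and the relative difficulty of conversion". Its formal endpoint is the SSQ12-C one month after crossover (SAP 1.4.2.2). SAP 1.6.2 names the acute ratings among supportive analyses that may be done.

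**The concern.** Loudness and intelligibility are two of the four rated attributes, and both depend on how loudly and clearly the passage is spoken. With a live talker neither is fixed, and with up to 7 sites the talker will vary. If the reader has just programmed the device, that person knows the strategy. The protocol also gives staff a directional expectation: its introduction reports problems converting from ACE to FAST, and section 9.2 says some experienced users struggled to adapt.

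At stake is the between-group reading in Protocol 5.1. Group 1 rates ACE against FAST, and Group 2 rates FAST against ACE. Each subject gives one comparative rating per attribute, so differences in delivery between subjects are not removed by the crossover.

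**Working it through.** The plan gives no standard deviation, effect size, test or sample size for these ratings. Its calculated sample sizes (8 for CNC, 11 for BKB) concern the co-primary endpoints and take no input from the ratings. The check is therefore a reading of the passages, plus algebra on where a delivery effect would go.

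**1. Who reads?** Section 5.2.3 names only the clinician. Three things point to the programmer: the reading follows mapping immediately (5.2.3), it sits in the programming step (5.5.4), and it takes place at the Clinical Site (Table 1). Endpoint testing may be at the sponsor's Denver laboratory, in which case the blinded tester is elsewhere. The programmer's knowledge of the strategy is also inferred: different firmware is loaded for each strategy (3.2), programming follows group, and 5.2.4 blinds only the subject's endpoint tester. Both inferences are strong, but neither is stated.

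**2. What is controlled?**

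| Feature | Other speech tests | Acute ratings (5.2.3) |
|---|---|---|
| Material | Recorded (5.2.4) | Read live |
| Level | 60 dBA for AzBio (5.2.1) and CNC; 65 dBA for BKB | Not stated |
| Configuration | Implant only (5.2.4) | Not stated |
| Program | Everyday | Everyday, if the rule in 5.2.2 for testing covers ratings |
| Administrator | Blinded, not the programmer (5.2.4) | Not stated |

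Configuration could matter because contralateral hearing varies enough to be listed as a covariate (SAP 1.6.1).

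**3. Is the first strategy heard again?** Section 5.1 speaks of direct comparison, but no step presents the passage under the first strategy, before or after reprogramming. Because the strategies use different firmware, switching back during the rating cannot be assumed.

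**4. Where would a delivery effect go?** Let Δ1 and Δ2 be the true mean ratings in Groups 1 and 2.
- A shift c common to both groups cancels in the signed contrast: (Δ1 + c) − (Δ2 + c) = Δ1 − Δ2. It still moves each group's mean away from its true value.
- Talker and level variation that differs independently between subjects, with variance σ², adds σ²(1/10 + 1/10) = 0.2σ² to the variance of the contrast with 10 per group. This is noise, not bias.
- A delivery that favours ACE by b points raises Group 1 and lowers Group 2: (Δ1 + b) − (Δ2 − b) = (Δ1 − Δ2) + 2b. If the sizes of change are compared instead, the shift is again 2b in magnitude when both groups rate the new strategy worse. It cancels when the true changes have opposite signs, with ACE preferred in both groups.

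Neither σ² nor b can be obtained from the documents, and the statistic to be compared is not specified.

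**5. How thin are the data per talker?** If all 7 sites recruited equally, each would have 20/7 ≈ 2.9 subjects. Section 5.1 describes random assignment without mentioning balance by site, so talkers need not be balanced across groups.

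**The case against.** The strongest reply is that subjects are blinded to strategy identity (Protocol 5.1). Clinician influence would have to reach a blinded rater through voice or manner and differ by group. Otherwise live voice adds only noise or a common shift. That is right, and it is why influence is only a possibility here.

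The recall gap is also short. Subjects have used the first strategy for three months, up to reprogramming, and the rating follows at once. Playing the passage before reprogramming still gives a comparison across the mapping session. This stands: the gain is a matched stimulus and less reliance on memory, not its removal.

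The safeguards in 5.2.4 are written for endpoint testing, so their absence from 5.2.3 is not a contradiction. The protocol is also modest: it claims some insight, says a group difference may indicate disparities, notes that FAST is already known to sound different, and adds the later questionnaire. Both points stand.

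Finally, naturalness is a rated attribute and a live talker is a defensible stimulus for a first impression. This carries some weight, but the rating compares strategies and the same recording would be heard under both.

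**Conclusion.** The point holds as a minor, inexpensive improvement. The ratings rest on a stimulus with no set level or listening configuration, most likely delivered by someone who knows the strategy, with no matching presentation under the first strategy. The between-group reading in Protocol 5.1, and through it part of the evidence on secondary objective 2, is exposed to talker and level variation and to possible clinician influence. The size is unknown.

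This rests on two inferences: that the reader is the programmer, and that the programmer knows the strategy.

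A reader might infer more, and the documents do not support it:
- That a recording alone would solve the problem. It fixes voice and level, but not memory or the way ratings are requested.
- That lip-reading contaminates the ratings. The protocol does not say whether the reader's face is visible.
- That the second secondary endpoint is compromised. That endpoint is the SSQ12-C. No success rule, alpha or power depends on the acute ratings.

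**What to change.** Amend Protocol 5.2.3 in three respects:
1. Use a recorded Rainbow Passage in the sound field at a stated fixed level, implant only, in the Everyday program. This standardises the stimulus.
2. At Visit 5, play it with the first strategy just before reprogramming and again after the second strategy is mapped. This reduces reliance on memory.
3. Have the subject complete the four ratings on a self-administered form. This limits influence when the ratings are collected.

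The cost is one recording and a few extra minutes at Visit 5. Clinical Sites already run sound-field AzBio testing at that visit (5.2.1, Table 1), so no new set-up, visit or staff is needed. The downside is a stimulus somewhat less natural than a live talker.

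If live voice is kept, 5.2.3 should at least state who reads, at what level, in what listening configuration, and whether the passage is also heard with the first strategy. SAP 1.6.2 needs no change.
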